This is an open trial pilot intervention study that involves: interviews, online surveys, online group video-conferencing intervention sessions, audio-recording of intervention sessions. The intervention will consist of 10 weekly 90-minute group supportive therapy sessions conducted via Zoom. Study outcomes will be both quantitative (surveys) and qualitative (interviews) in nature.

Study Duration

The entire study, including data analysis, is expected to last from August 2021 until August 2022. Participation for the subjects will begin in August 2021 (i.e., recruitment, pre-intervention assessment). Participants in the first group will begin the 10-week intervention in September-November 2021 and complete their post-intervention assessment in December 2021-January 2022. Participants in the second group will begin the 10-week intervention in February 2022 and complete their post-intervention assessment in May 2021-June 2022. Data analysis is expected to continue through August 2022.

Outcome Variables

Primary Objective:

- Acceptability:
 - *Main outcome*: Client Satisfaction Questionnaire-8 (CSQ-8)
 - Supportive variables: Treatment Expectations, Top Problems Assessment, Top Problems Tracking Form, Acceptability of Session Questionnaire, AFFIRM Acceptability Survey, Exit Interview-Acceptability of program format, delivery, and content
- Feasibility:
 - *Main outcome*: Session Attendance
 - Supportive variables: Homework Compliance Scale, Feasibility of Session Questionnaire, Feasibility of Program Questionnaire, Exit Interview-Program feasibility
- Need for refinement:
 - Main outcome: Exit interview
 - Supportive variables: Session Refinement Questions, Program Refinement Questions

Secondary Objective:

- Mental health:
 - Main outcome: Revised Children's Anxiety and Depression Scale (RCADS)
 - Supportive variables: Depressive Symptom Index Suicidality Subscale (DSI-SS), Strengths and Difficulties Questionnaire (SDQ), WHO-5 Well-Being Index
- Minority stress reactions:
 - Main outcome: Gender Minority Stress and Resilience Scale for Adolescents (GMSR-A) — Internalized Trans/Homophobia subscale
 - Supportive/related variables: Rest of GMSR-A, Child Perceived Discrimination Questionnaire (CPDQ), Outness Inventory (OI), Lesbian, Gay, Bisexual Affiliate Stigma Measure (LGB-ASM), Parental Rejection/Acceptance of LGBTQ child
- Emotion regulation & coping:
 - Main outcome: Children's Emotion Management Scales (CEMS)

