The intervention itself will consist of 10 weekly, 90-minute group sessions, delivered remotely via Zoom. The intervention will be delivered by [name] [name], who has experience counseling LGBTQ teenagers and who has received training in the intervention from the PI (who developed LGBTQ-affirmative CBT), with support from the study team. Intervention sessions and associated home practice will cover the following topics (additional details are provided in the Session Outlines document uploaded in IRES):

- Building and keeping motivation
- Introduction to LGBTQ-related stress
- Getting to know your emotions
- Introduction to emotional behaviors and behavioral experiments
- Awareness of physical sensations and introduction to flexible thinking
- Being flexible in your thinking
- Awareness of emotional experiences
- Assertiveness
- Situational exposures
- Reviewing accomplishments and looking ahead

Participants will be taught intervention content through a range of teaching modalities including use of the Zoom whiteboard feature, videos, interactive activities, worksheets, and

group discussion. All sessions will be audio-recorded for supervision purposes, and audio recordings will be saved in a secure Yale Box folder.

Following each intervention session, participants will be sent a brief survey to evaluate the acceptability, feasibility, and need for refinement of each intervention session. Participants will also complete brief mental health measures each week to address the study's secondary objective. Participants will be asked to submit an electronic copy (e.g., PDF, photo) of any completed home practice assignments to the study team via Yale's Secure File Transfer, in order to evaluate the acceptability of these assignments. Study staff will de-identify all home practice materials before saving them in a secure Yale Box folder with the participant's study ID number.

Post-intervention assessment measures will be sent to youth participants and their parent/caregiver immediately following the last intervention session, and will be available for three weeks (see 4.2 for full list of measures). After the post-intervention assessment is complete, youth will be invited to complete an exit interview via Zoom/phone to assess the feasibility, acceptability, and refinement.

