4.2.1 Primary Outcome Variables/Endpoints

Acceptability:

• *Client Satisfaction Questionnaire-8 (CSQ-8).* The CSQ-8 (Larsen et al., 1979) is a well-validated, 8-item self-report questionnaire designed to assess patient/client satisfaction with services received. Both the adolescent self-report and the parent report of child services versions of the CSQ-8 will be used in this study. Items are scored on a 4-point scale, where higher scores indicate more satisfaction. The CSQ-8 has demonstrated excellent internal consistency in prior studies (α = 0.93; Larsen et al., 1979).

Feasibility:

• Session Attendance. Session attendance will be tracked by the study therapist(s) each week to examine the feasibility of weekly sessions.

Need for refinement:

• *Exit Interview.* The need to refine the intervention will also be assessed qualitatively during a post-intervention exit interview with each youth participant. Questions will probe participants' suggestions for improving the intervention, as well as the parts of the intervention that they felt most helpful, among other topics.

Mental health:

Revised Children's Anxiety and Depression Scale (RCADS). The RCADS (Chorpita et al., 2000; Ebesutani et al., 2010) is a 47-item questionnaire assessing symptoms of depression and anxiety in youth aged 6-18 years. Both the parent-report and the child self-report versions of this scale will be used in this study. In addition to a Total Internalizing Scale and a Total Anxiety Scale, the RCADS includes six subscales: separation anxiety disorder (SAD), social phobia (SP), generalized anxiety disorder (GAD), panic disorder (PD), obsessive compulsive disorder (OCD), and major depressive disorder (MDD). Items are rated on a 4-point Likert-scale from 0 ("never") to 3 ("always"). Previous studies have showed the RCADS has good internal consistency (αs = 0.73-0.82; Chorpita et al., 2000).

Minority stress reactions:

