Intervention: Each week for ten weeks, youth participants will attend a 90-minute group therapy session via Zoom. Participants will be taught intervention content (see Session Outlines document uploaded in IRES for more details) through a range of teaching modalities including use of the Zoom whiteboard feature, videos, interactive activities, worksheets, and group discussion. The intervention will be delivered by [name] [name], who has experience counseling LGBTQ teenagers and who has received training in the intervention from the PI (who developed LGBTQ-affirmative CBT), with support from the study team. To ensure fidelity to the intervention model, [name] [name] will engage in clinical supervision with the PI throughout the course of the intervention, and any inadequate fidelity to the intervention model will be addressed during these supervision meetings. All sessions will be audio-recorded for supervision purposes, and audio recordings will be saved in a secure Yale Box folder. Due to the need for clinical supervision given the pilot nature of this intervention, audio recording will be a mandatory aspect of the study. Participants and their parent/caregiver will be informed of this requirement during the informed consent process.

Weekly assessments: Following each intervention session, youth participants will be sent a brief survey to evaluate the acceptability, feasibility, and need for refinement of each intervention session. Participants will also complete brief mental health measures each week to address the study's secondary objective. Participants will be asked to submit an electronic copy (e.g., PDF, photo) of any completed home practice assignments to the study team via Yale's Secure File Transfer, in order to evaluate the acceptability of these assignments. Study staff will de-identify all home practice materials before saving them in a secure Yale Box folder with the participant's study ID number. For the first two weekly assessments, a study team member will call the youth participant to ensure that they understand all the survey questions and to ensure that responses via both modalities (i.e., phone, online survey) are consistent.

Post-intervention assessment: Post-intervention assessment measures will be sent to youth participants and their parent/caregiver immediately following the last intervention session, and will be available for three weeks (see 4.2 for full list of measures).

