Exit interview: Once all other study tasks are complete, exit interviews will be conducted with youth via Zoom/phone to assess the feasibility, acceptability, and need for refinement of the intervention. See Measure Packet uploaded in IRES for exit interview content.

Unscheduled visits: We do not anticipate any unscheduled intervention visits outside of the regularly scheduled group therapy sessions. However, in the event that participants indicate suicidality on any of the assessment surveys, the clinical protocol for our lab will be initiated (as described in 6.4), which requires a study team member to reach out to the participant via phone or Zoom to complete a safety assessment. In addition, if a youth participant does not show up to their scheduled visit, a study team member will contact the participant and/or their parent/legal guardian by phone/Zoom to assess barriers to attendance

Visit Schedule

C = Child P = Parent T = Therapist	Screening surveys Day -14 to 0	Diagnostic interview / Consent Call Day 1	Pre-intervention Day 14 ± 7	Session 1 Day 28 ± 7	Session 2 Day 35 ± 7	Session 3 Day 42 ± 7	Session 4 Day 49 ± 7	Session 5 Day 56 ± 7	Session 6 Day 63 ± 7	Session 7 Day 70 ± 7	Session 8 Day 77 ± 7	Session 9 Day 84 ± 7	Session 10 Day 91 ± 7	Post-intervention Day 91 ± 21	Exit interview Day 98 ± 42
Consent / Assent / Permission	С, Р	С, Р													
Background Information															
Demographics	С, Р														
Gender Unicorn			С											C	
Parent-Child Relationship			Р											Ρ*	
FAD			С, Р											С, Р	
Acceptability															
Treatment Expectations			С												
Top Problems Assessed				С											
Top Problems Tracking					C	C	С	C	C	С	C	С	С	C	
CSQ-8								C						С, Р	
Acceptability of session				C	C	C	C	C	C	C	C	С	С		
AFFIRM Acceptability														С, Р	
Format/delivery/content															C
Feasibility															
Session Attendance				Т	Т	Т	Т	Т	Т	Т	Т	Т	Т		
Homework Compliance				Т	Т	Т	Т	Т	Т	Т	Т	Т	Т		
Feasibility of Session				С	C	C	С	C	C	С	С	С	С		
Feasibility of Program														Р	C
Need for Refinement															
Session Refinement				C	C	C	C	C	C	C	C	С	C		

Program Refinement														Р	C
Mental Health															
KSADS		С, Р													
RCADS - Long	С, Р		С, Р											С, Р	
RCADS - Short				С	С	С	С	С	С	C	C	С	С		
DSI-SS		С	С	С	С	С	С	С	С	C	C	С	С	C	
SDQ			С, Р											С, Р	
WHO-5 Well-Being Index			C											C	
CRAFFT 2.1			C											C	
AQ-10			Р												

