Exit-interviews will be conducted via Zoom following the completion of the last intervention session and the post-intervention assessment. Audio recordings of the exit-interviews will be saved in a secure Yale Box folder, and transcripts will be created of the interview data (also saved on Box). Following the verification of the transcripts, the original audio files of the interviews will be deleted, and the transcripts will be de-identified.

The study participant's contact information will be securely stored for internal use during the study. At the end of the study, all records will continue to be kept in a secure location for three years. After three years, all identifiable records for the study will be destroyed.

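### The exit interview is timed by completion of other study tasks, so youth who stop sessions and do not return the final survey may never be invited

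*Combined protocol and SAP*

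**What the plan says.** The Synopsis lists the interview under need for refinement as "Main outcome: Exit interview" and as a supportive variable for acceptability and feasibility. Section 4.2.1 says that need for refinement is "assessed qualitatively during a post-intervention exit interview with each youth participant". Section 4.2.2 repeats that coverage for acceptability and feasibility. Section 7.2 uses the interviews to find what helped and what hindered feasibility and acceptability, and which parts need changing.

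Three places say when the interview happens:

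- Section 4: "After the post-intervention assessment is complete, youth will be invited to complete an exit interview via Zoom/phone"
- Section 6.1: "Once all other study tasks are complete, exit interviews will be conducted with youth via Zoom/phone"
- Section 6.1.1: "Exit-interviews will be conducted via Zoom following the completion of the last intervention session and the post-intervention assessment"

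The survey that comes before it is sent "immediately following the last intervention session, and will be available for three weeks" (section 6.1). The Visit Schedule prints "Exit interview Day 98 ± 42".

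For a missed visit, section 6.1 says that "a study team member will contact the participant and/or their parent/legal guardian by phone/Zoom to assess barriers to attendance". Section 6.5 allows withdrawal at any time and destruction of data on request, and does not mention an interview. Section 8.2 limits follow-up of missed assessments to two reminders.

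**The concern.** The sections that say who is interviewed and the sections that say when do not fit together for one group: enrolled youth who stop attending, do not return the post-intervention survey, and have not withdrawn from contact. The first set includes them. The second, followed to the letter by the staff who schedule interviews, never reaches them.

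These youth are well placed to say what made the programme unworkable or unappealing. Without them, the main outcome for need for refinement and the section 7.2 search for hindering factors would lean towards those who stayed. Analysing all available data without imputation (section 7.7) cannot recover an interview that was never held. Section 2.1 presents the pilot as preparation for a larger efficacy trial, so what it misses may be carried forward.

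Loss of interviews through withdrawal or a request to destroy data follows from a participant's right and is not part of this point.

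**Working it through.** **Who is invited under each wording.** The second column takes the completion wording literally, youth by youth. The third takes it as a calendar order.

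| Enrolled youth | Literal reading | Calendar reading |
|---|---|---|
| Attends to the end, returns survey | Invited | Invited |
| Stops sessions, returns survey | Invited under section 4; unclear under 6.1 and 6.1.1 | Invited |
| Stops sessions, does not return survey | Not invited under any of the three | Invited |

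No passage says which reading is meant. The third row is the gap.

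**Inputs (Visit Schedule, section 6.1).** Session 1 on Day 28, then weekly; Session 10 on Day 91 ± 7; post-intervention Day 91 ± 21; exit interview Day 98 ± 42. The survey stays open for three weeks after the last session.

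**Reproducing the schedule.** Session 10 = 28 + 7 × 9 = Day 91, as printed.

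**Is there time to interview non-responders?**

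- Survey close, nominal: 91 + 21 = Day 112
- Survey close, latest Session 10: (91 + 7) + 21 = 98 + 21 = Day 119
- Interview window closes: 98 + 42 = Day 140
- Time left after survey close: 140 − 112 = 28 days, or 140 − 119 = 21 days at the latest

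So a rule that invites non-responders once the survey closes fits inside the printed window.

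**How long an early leaver would wait for that.** From Session 1 (Day 28): 112 − 28 = 84 days. From Session 4 (Day 49): 112 − 49 = 63 days. Survey close is therefore better set as the latest time for an invitation than as the only one.

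**Printed windows against the stated order.**

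- Interview window opens: 98 − 42 = Day 56
- Earliest Session 10: 91 − 7 = Day 84, so the window opens 84 − 56 = 28 days earlier
- Post-intervention window opens: 91 − 21 = Day 70, also before Session 10, although that survey is sent only after it
- Post-intervention window closes on Day 112, which is 119 − 112 = 7 days short when Session 10 falls on Day 98

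If ± was meant as +, the windows become Day 91–112 and Day 98–140, and neither opens before the nominal Session 10.

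**The case against.** The strongest reply is that the three timing sentences give a sequence and not an entry condition. Sections 4.2.1 and 4.2.2 speak of each youth, and section 7.2 of all participants' data. Section 5.5 lists the $30 interview payment separately, with no condition on the survey. Sessions are group events on a fixed calendar, and the survey goes to youth after the last one with no attendance condition, so completion may simply mean that the date has passed. Read strictly, the section 6.1 wording would also bar a youth who skipped one weekly survey, which can hardly be intended. This stands as a plausible reading. It does not settle the matter, because no sentence says so and staff must choose.

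Partial cover also stands. Therapist-recorded attendance, the main feasibility outcome, is unaffected. Weekly feedback forms are analysed inductively (section 7.4). Youth complete the CSQ-8 at Session 5. Parents are sent the Feasibility of Program Questionnaire and the CSQ-8 with no stated dependence on the youth's attendance. The no-show call asks directly about barriers. The cover has limits. A youth who leaves before Session 5 may have no CSQ-8, families who leave may not return the parent survey, and no section says that the barriers given in calls are analysed.

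A reader might infer more than the documents support:

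- *Early leavers are excluded by design.* No exclusion is stated, and the coverage sentences point the other way.
- *Reasons given in no-show calls are certainly not kept.* The text is silent. Section 8.4 omits the calls from the study records, but it omits the exit interviews too, so that list proves nothing. The attached clinical protocol and measures packet are not available here.
- *Fewer than 20 interviews would miss saturation.* Section 7.1 does not say so. Subtracting an assumed number of leavers from 20 would only restate the assumption.
- *Interviews would be held mid-programme because the window opens on Day 56.* The text order prevents this, and no analysis uses the window. It is probably loose notation.

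**Conclusion.** The point holds as an ambiguity with a plausible consequence. On the literal reading, an enrolled youth who stops sessions and does not return the survey has no route to the interview, and the evidence on need for refinement and on hindering factors could rest on completers. On the calendar reading there is no gap, but the plan does not say that this is what it means.

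The effect cannot be sized: the documents give no dropout or survey-return rate, and a shift in interview themes is not computable from them. The conclusion assumes only that some youth stop without withdrawing from contact and that staff may follow the timing sentences as written. This is a change worth considering. It does not undermine the pilot, and the printed windows are an editorial matter.

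**What to change.** In sections 4, 6.1 and 6.1.1, state one rule: every enrolled youth who has not withdrawn from contact is invited to the exit interview whatever sessions or surveys they completed, at the latest once the three-week survey period closes. Keep this within the rights in section 6.5 and in line with the two-reminder limit in section 8.2. A rule to interview at the moment of stopping is not proposed. It would need a definition of stopping, which the protocol lacks, and a youth who misses sessions may return.

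Record the barriers given in no-show calls as feasibility data. Report the number interviewed out of the number enrolled by completion status (sessions attended, survey returned or not). As an editorial step, reconcile the printed post-intervention and exit-interview windows with the stated order.

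The cost is an IRB amendment (section 9.1) and modest staff time. The one-hour interview and its payment are already in section 5.5, and the no-show call is already in section 6.1. Some early leavers will still decline, so the gap would narrow without closing, and the reported counts would show by how much.

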6.1.1 Data Collection

All survey-based data collection will occur online via the secure Yale Qualtrics survey software. Such data collection will begin with the initial online screening surveys, to be completed by both parent/caregiver and the potential youth participant. Specific details about the contents of the screening surveys are provided elsewhere in this document; briefly, questions pertaining to the inclusion and exclusion criteria for this study will be asked in order to determine eligibility for the study. In addition, identifiable contact information (including parent/caregiver and youth name, email address, physical address and phone number) will be collected in these screening surveys in order to facilitate contacting participants for the diagnostic interview stage of the screening process. If, after the parent/caregiver completes their screening survey, it is clear that their child will not be eligible for the study, no contact information will be requested, in order to maximize potential participant confidentiality.

After participants have completed the screening surveys through Qualtrics, a study team member will reach out potentially eligible participants (by phone and/or email) to schedule a one-hour call (Zoom or phone) for a brief diagnostic interview with [name] [name] (lead postdoctoral associate). [name] [name] will administer relevant modules from the Kiddie Schedule for Affective Disorders and Schizophrenia (K-SADS), in order to confirm the youth meets diagnostic criteria for a DSM-5 internalizing disorder. Administration of the K-SADS requires advanced training, which [name] [name] received from a doctoral-level supervisor in a prior role. She has 6 years of experience administering the K-SADS to more than 100 youth and their families. [name] [name] will record the youth and parent responses to the interview questions on a separate PDF copy of the KSADS for each participant, which will be saved after the interview on a secure Yale Box folder. In addition, diagnostic findings of the KSADS will be recorded in a de-identified spreadsheet saved in a secure Yale Box folder.

All participants will be given a unique code that will serve as their study ID for the duration of the study. The use of the unique code will permit linkage of the data being collected across time points in the study. A master link file will connect participant names, phone numbers, email addresses, and physical addresses to their study code number. The link file will be password protected and only accessible to the study team as required for study tasks (e.g., providing participants with intervention-related materials). All data collection materials will be stored on password-protected folders on Yale Secure Box that requires dual-factor authentication to access.

Pre-intervention assessment measures will be sent to youth participants and their parents via Qualtrics within two weeks of the first intervention session.

All intervention sessions will be audio-recorded for supervision purposes, and audio recordings will be saved in a secure Yale Box folder. De-identified transcripts will be created of the interview data (also saved on Box).

Weekly assessments will be sent via Qualtrics to youth immediately following each intervention session. In addition, the study therapist ([name] [name]) will complete a weekly post-intervention Qualtrics survey tracking each participant's attendance and homework compliance for the previous week. Participants will be asked to submit an electronic copy (e.g., PDF, photo) of any completed home practice assignments to the study team via Yale's Secure File Transfer, in order to evaluate the acceptability of these assignments. Study staff will de-identify all home practice materials before saving them in a secure Yale Box folder with the participant's study ID number. In line with the clinical protocol, home practice assignments will be reviewed by the study team within 24 hours or the next business day to assess for any report of harm to self or others.

Post-intervention assessment measures will be sent to youth participants and their parents immediately following the last intervention session, and will be available for three weeks. None of the measures in these surveys require licensure for their administration. All measures can be found in the "Measures Packet" uploaded with the study protocol.

Exit-interviews will be conducted via Zoom following the completion of the last intervention session and the post-intervention assessment. Audio recordings of the exit-interviews will be saved in a secure Yale Box folder, and transcripts will be created of the interview data (also saved on Box). Following the verification of the transcripts, the original audio files of the interviews will be deleted, and the transcripts will be de-identified.

The study participant's contact information will be securely stored for internal use during the study. At the end of the study, all records will continue to be kept in a secure location for three years. After three years, all identifiable records for the study will be destroyed.

